11.0 Safety Analysis

11.1 General Considerations

All subjects who receive at least one dose of study drug in Study M14-423 will be included in the safety analyses.

11.2 Analysis of Adverse Events

11.2.1 Treatment-Emergent Adverse Events

Adverse events will be coded using the Medical Dictionary for Regulatory Activities (MedDRA). Treatment-emergent adverse events are defined as any event that begins or worsens in severity after initiation of study drug through 30 days after the last dose of study drug. Events where the onset date is the same as the study drug start date are assumed to be treatment-emergent. If an incomplete onset date was collected for an adverse event, the event will be assumed to be treatment-emergent, unless there is other evidence that confirms that the event was not treatment-emergent (e.g., the event end date was prior to the study drug start date).

11.2.1.1 Tabulations of Treatment-Emergent Adverse Events

Adverse event data will be summarized and presented using primary MedDRA system organ classes (SOCs) and preferred terms (PTs) according to the version of the MedDRA coding dictionary used for the study at the time of database lock. The actual version of the MedDRA coding dictionary used will be noted in the clinical study report. The system organ classes will be presented in alphabetical order and the preferred terms will be presented in alphabetical order within each system organ class.

Adverse Event Overview

An overview of adverse events will be presented consisting of the number and percentage of subjects experiencing at least one event for the following adverse event categories:

- Any treatment-emergent adverse event;

- Treatment-emergent adverse events with a "reasonable possibility" of being related to DAAs;
- Treatment-emergent adverse events with a "reasonable possibility" of being related to RBV;
- Severe treatment-emergent adverse events;
- Serious treatment-emergent adverse events;
- Treatment-emergent adverse events leading to discontinuation of study drug;
- Treatment-emergent adverse events leading to interruption of study drug;
- Treatment-emergent adverse events leading to RBV dose modifications;
- Treatment-emergent adverse events leading to death;
- Deaths.

Adverse Event by SOC and PT

The following summaries of adverse events will be generated:

- Treatment-emergent adverse events;
- Treatment-emergent adverse events with a "reasonable possibility" of being related to DAAs;
- Treatment-emergent adverse events with a "reasonable possibility" of being related to RBV;
- Serious treatment-emergent adverse events;
- Moderate or severe treatment-emergent adverse events;
- Severe treatment-emergent adverse events;
- Grade 3 or 4 (see definition below) treatment-emergent adverse events;
- Treatment-emergent adverse events leading to discontinuation of study drug;
- Treatment-emergent adverse events leading to interruption of study drug;
- Treatment-emergent adverse events leading to RBV dose modifications;
- Treatment-emergent adverse events leading to death;
- Treatment-emergent adverse events leading to concomitant medication use (events with other action taken of "concomitant medication prescribed").

For all adverse event summaries, the number and percentage of subjects experiencing treatment-emergent adverse events will be tabulated according to SOC and PT. Subjects reporting more than one adverse event for a given PT will be counted only once for that term (most severe incident for the severity tables and most related incident for the relationship tables). Subjects reporting more than one adverse event within a SOC will be counted only once for that SOC. Subjects reporting more than one adverse event will be counted only once in the overall total.

A listing of treatment-emergent adverse events grouped by body system and preferred term with subject numbers will be created.

Adverse Event by PT

The number and percentage of subject experiencing treatment-emergent adverse events will be tabulated according to preferred term and sorted by overall frequency. Similar summaries will be provided for moderate to severe treatment-emergent adverse events and treatment-emergent adverse events with a "reasonable possibility" of being related to DAAs.

Adverse Event of Special Interest

Specific treatment-emergent adverse events of special interest, which may be searched using Standardized or Company MedDRA Queries, will be summarized. The search criterion for the adverse event of interest is as follows:

- Hepatic Decompensation and Hepatic Failure
PMQ "Hepatic decompensation and hepatic failure"

The number and percentage of subjects experiencing at least one treatment-emergent adverse event in the search for the event of interest will be presented by SOC and PT.

A listing of treatment-emergent adverse events for subjects meeting the search criterion will be provided for the adverse event of special interest.

Adverse Event by Maximum Severity

Treatment-emergent adverse events and treatment-emergent adverse events with a "reasonable possibility" of being related to DAAs will be summarized by maximum severity of each preferred term. If a subject has an adverse event with unknown severity, then the subject will be counted in the severity category of "unknown," even if the subject has another occurrence of the same event with a severity present. The only exception is if the subject has another occurrence of the same adverse event with the most extreme severity – "Severe." In this case, the subject will be counted under the "Severe" category.

Adverse Events by Maximum Severity Grade Level

Treatment-emergent adverse events will be summarized by maximum severity grade level of each preferred term. Each preferred term will be assigned to a grade level based on severity and seriousness, adapted from the Division of AIDS (DAIDS) table for grading severity of adverse events. All serious adverse events will be categorized as Grade 4. Nonserious adverse events categorized by the investigators as mild, moderate, or severe will be categorized as Grade 1, Grade 2, or Grade 3, respectively. If a subject has a nonserious adverse event with unknown severity, then the subject will be counted in the severity grade level category of "unknown," even if the subject has another occurrence of the same event with a severity present. The only exception is if the subject has another occurrence of the same adverse event with the most extreme severity – "Severe." In this case, the subject will be counted under the "Grade 3" category. Similarly, if a subject has an adverse event with unknown seriousness, then the subject will be counted in the severity grade level category of "unknown" unless the subject has another occurrence of the same adverse event that is marked serious. In this case, the subject will be counted under the "Grade 4" category.

Adverse Event by Maximum Relationship

Treatment-emergent adverse events also will be summarized by maximum relationship of each preferred term to DAA study drug and RBV, as assessed by the investigator. If a subject has an adverse event with unknown relationship, then the subject will be counted

in the relationship category of "unknown," even if the subject has another occurrence of the same event with a relationship present. The only exception is if the subject has another occurrence of the same adverse event with a relationship assessment of "Reasonable Possibility." In this case, the subject will be counted under the "Reasonable Possibility" category.

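### In the maximum-grade adverse-event table, the unknown-severity rule takes a subject with a serious (Grade 4) event out of Grade 4

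*SAP*

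**What the plan says.** The paragraph on maximum severity grade level in SAP 11.2.1.1 sets out the table in these steps.

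- **Unit.** "Treatment-emergent adverse events will be summarized by maximum severity grade level of each preferred term".
- **Grades.** "All serious adverse events will be categorized as Grade 4". For an event that is not serious, the investigator's rating of mild, moderate or severe becomes Grade 1, 2 or 3.
- **Unknown severity.** "If a subject has a nonserious adverse event with unknown severity, then the subject will be counted in the severity grade level category of". The category named there is *unknown*, and the subject is put in it "even if the subject has another occurrence of the same event with a severity present".
- **Exception to that.** "The only exception is if the subject has another occurrence of the same adverse event with the most extreme severity", namely *Severe*. Such a subject goes to Grade 3.
- **Unknown seriousness.** "Similarly, if a subject has an adverse event with unknown seriousness, then the subject will be counted in the severity grade level category of". Here too the category is *unknown*, except that a subject with a further occurrence marked serious is Grade 4.

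Earlier in the same section, the general counting rule says that a subject with several events of one preferred term is counted once, by the most severe incident in the severity tables.

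**The concern.** The unknown-severity rule names one exception and calls it the only one. That exception stops at *Severe*, which is the top level of the investigator's severity scale but not of the grade scale used here, where a serious event is Grade 4. The override that restores Grade 4 is written only for the separate case of unknown seriousness.

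A subject with one serious and one nonserious occurrence of a term, the second lacking a severity, thus falls under a rule that contradicts both the grading of serious events and the maximum principle. At stake is the Grade 4 row of a descriptive safety table. It could disagree with the serious-event table for the same term, and two programmers, one following the text and one following the evident intent, would get different counts.

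**Working it through.** The documents give no figure for this point, so there is none to reproduce. The check has three parts.

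**1. Can the missing value change the maximum?** A nonserious event is Grade 1, 2 or 3. With a serious occurrence present, the maximum is max(4, x) with x at most 3, which is 4 whatever the missing severity was. Assigning *unknown* makes sense only when the missing value could raise the maximum. Here it cannot.

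**2. What does the rule give, case by case?** Each occurrence has a seriousness (yes, no, unknown) and a severity (mild, moderate, severe, unknown), so there are 3 × 4 = 12 types. Unordered pairs number 12 × 13 / 2 = 78. Pairs with no serious occurrence number 8 × 9 / 2 = 36. That leaves 78 − 36 = 42 pairs with at least one serious occurrence. Applying the text literally, 38 give Grade 4 and 4 do not:

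| Serious occurrence rated | Other occurrence | Category as written | Maximum grade |
|---|---|---|---|
| mild | nonserious, severity unknown | unknown | 4 |
| moderate | nonserious, severity unknown | unknown | 4 |
| unknown | nonserious, severity unknown | unknown | 4 |
| severe | nonserious, severity unknown | Grade 3 | 4 |

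Pairs in which the other occurrence has unknown seriousness all give Grade 4, because the override covers them. If a serious occurrence is tested first, all 42 pairs give Grade 4.

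The two rules can also collide. Take a subject with one serious occurrence, one of unknown seriousness and one nonserious of unknown severity, none rated severe. One rule gives Grade 4 and the other gives *unknown*, and no precedence is stated.

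**3. How many subjects could be affected?** Inputs:
- 1650 subjects, with F4 subjects limited to about 400 (Protocol 5.1; SAP 4.2). I assume the limit is reached, leaving 1650 − 400 = 1250 others.
- Serious-event rates from Protocol Table 2: 4.7% (24 weeks) and 6.3% (12 weeks) in cirrhotics; 1.4% to 2.2% across the active arms without cirrhosis.

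Expected subjects with a serious event:
- Low: 400 × 4.7% + 1250 × 1.4% = 18.8 + 17.5 = 36.3
- High: 400 × 6.3% + 1250 × 2.2% = 25.2 + 27.5 = 52.7

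So about 36 to 53 subjects. To be misgraded, a subject must also have a nonserious occurrence of the same preferred term with severity missing. The documents give no rate for that, so the final count cannot be calculated.

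**The case against.** The best defence is that the intent is clear from the surrounding text. Serious events are Grade 4 without condition, the general counting rule takes the most severe incident, and the unknown-seriousness sentence lets a serious occurrence prevail over missing data. The disputed rule directly follows the grading of nonserious events, so it might be meant for nonserious occurrences only. This is good evidence of what was intended. It does not rescue the wording: the rule allows a single exception, and a serious occurrence is not it.

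The trigger should also be rare. Protocol 6.0 and 6.2 have the investigator rate the severity of each event, Protocol 10.2 has the eCRFs reviewed for completeness, and the data are cleaned before lock. That stands and limits the size.

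Four stronger readings are tempting, and the documents do not support them.

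- **That the Grade 3 or 4 table is undercounted.** SAP 11.2.1.1 lists that table without saying whether it selects events by grade or uses the subject-level category. If it selects events, a serious event enters as Grade 4 and nothing changes. Even on the subject-level reading, the subject moved to Grade 3 stays in that table.
- **That serious events are hidden.** Serious treatment-emergent events appear in the overview, have their own table by system organ class and preferred term, and are listed under SAP 11.2.2.
- **That the rule only ever moves subjects out of Grade 4.** It also sends Grade 1 and 2 subjects to *unknown*, which is coherent, since the missing severity could be higher. Only among subjects with a serious occurrence is any misclassification necessarily downward from Grade 4.
- **That about 100 subjects are exposed.** That figure comes from 1650 × 6.3% = 104, which applies a cirrhotic rate to everyone despite the limit of about 400. Nor does a serious event alone bring the rule into play.

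**Conclusion.** Wrong as written. This is a stated rule that yields the wrong category, not merely a missing detail. It looks like the exception from the maximum-severity paragraph carried over to a scale with one more level. In the maximum-severity and maximum-relationship paragraphs, and in the unknown-seriousness rule, the top category overrides *unknown*; only this rule stops one level short.

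The consequence is confined to the maximum-grade table unless the Grade 3 or 4 table uses the subject-level category. No endpoint, estimate or test is touched. With about 36 to 53 subjects expected to have a serious event, the number actually misgraded is probably none to a few. That last statement is a judgement, resting on the assumption that severity is seldom missing.

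**What to change.** In the maximum-severity-grade paragraph of SAP 11.2.1.1, before the rule on unknown severity, add:

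> A subject with any serious occurrence of the preferred term is counted as Grade 4. The rule for unknown severity, including its Severe-to-Grade-3 exception, applies only to subjects with no serious occurrence of that term.

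This also settles the collision between the two rules. It would help to add a few words saying whether the Grade 3 or 4 table selects events or uses the subject-level category.

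The cost is one sentence in the SAP and one reordered condition in the table program. Data collection, endpoints and clinical procedures are unchanged, and I see no downside.

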## **6.3 Relationship to Study Drug**

The investigator will use the following definitions to assess the relationship of the adverse event to the use of study drug:

Reasonable Possibility	An adverse event where there is evidence to suggest a causal relationship between the study drug and the adverse event.
No Reasonable Possibility	An adverse event where there is no evidence to suggest a causal relationship between the study drug and the adverse event.

For causality assessments, events assessed as having a reasonable possibility of being related to the study drug will be considered "associated." Events assessed as having no reasonable possibility of being related to study drug will be considered "not associated." In addition, when the investigator has not reported a causality or deemed it not assessable, AbbVie will consider the event associated.

[figure not shown]
If an investigator's opinion of no reasonable possibility of being related to study drug is given, an Other cause of event must be provided by the investigator for the serious adverse event.

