6.3 Missing Data Imputation

No data will be imputed for any efficacy or safety analyses except for the PRO questionnaires, for analyses of the HCV RNA endpoints, and for analysis of the persistence of resistance. If a respondent answers at least 50% of the items in a multi-item scale of the SF-36v2, the missing items will be imputed with the average score of the answered items in the same scale. In cases where the respondent did not answer at least 50% of the items, the score for that domain will be considered missing. Similarly, the missing items of the FACIT-F questionnaire will be imputed with the average score of the answered items in the same scale as long as more than 50% (≥ 7 out of 13) of the items in the scale are answered. The SF-36v2 Mental and Physical Component Summary measures will not be computed if any domain is missing.

HCV RNA values will be selected for an SVR analysis based on visit windows as defined in Section 6.2. When there is no HCV RNA value in a visit window based on defined visit windows, the closest values before and after the window, regardless of the value chosen for the subsequent and preceding window, will be used for the flanking imputation described below.

If a subject has a missing HCV RNA value at a post-Day 1 visit but with undetectable or unquantifiable HCV RNA levels at both the preceding value and succeeding value, the HCV RNA level will be considered undetectable or unquantifiable, respectively, at this visit for this subject. In addition, if a subject has an unquantifiable HCV RNA level at the preceding value and an undetectable HCV RNA level at the succeeding value, or vice versa, the HCV RNA level will be imputed as unquantifiable at this visit for this subject. For SVR analyses, if there is no value in the appropriate window after flanking imputation but there is an HCV RNA value after the window, then it will be imputed into the SVR window. Subsequent to this flanking and backward imputation, if a subject is missing a value for the visit window associated with the analysis, the subject will be imputed as a visit failure (i.e., not undetectable or unquantifiable).

If a subject starts another treatment for HCV, then all HCV RNA and PRO assessment values for this subject measured on or after the start date of the new HCV treatment will be excluded from analyses. The subject will be considered a failure for summaries of viral response at all time points after the start of the new HCV treatment.

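### The SAP tabulates adverse events without a causality assessment as *unknown*, while the protocol classes them as associated; if any remain at lock, related-event counts can only be equal to or lower than the protocol's rule gives.

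*SAP*

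**What the plan says.** Protocol 6.3 has two causality classes, reasonable possibility and no reasonable possibility. The first is treated as associated with study drug and the second as not associated. A default then covers the gap: "when the investigator has not reported a causality or deemed it not assessable, AbbVie will consider the event associated". The protocol's definition of study drug (Section 1.3) includes the DAAs and ribavirin.

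SAP 11.2.1.1, under the heading on maximum relationship, summarises the "maximum relationship of each preferred term to DAA study drug and RBV, as assessed by the investigator". Its rule for a record without an assessment opens "If a subject has an adverse event with unknown relationship, then the subject will be counted" and sends that person to a separate *unknown* class, which overrides a recorded assessment of no reasonable possibility for the same term. The single exception is another occurrence of the same event assessed as a reasonable possibility: "In this case, the subject will be counted under the 'Reasonable Possibility' category".

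The same SAP section also plans summaries limited to related events. One is headed "Treatment-emergent adverse events with a 'reasonable possibility' of being related to DAAs", and there is a matching one for ribavirin. Both appear in the overview and in the SOC and preferred-term tables. The DAA-related events are tabulated again by preferred term alone and by maximum severity. None of these entries mentions missing causality.

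**The concern.** The two documents assign one record to different classes. The SAP neither cites the protocol default nor gives a reason for leaving it, and its choice is the less conservative one. An event could be associated in the sponsor's own classification and yet be missing from its tables of related events.

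This matters more in a single-arm, open-label study (Protocol 3.1 and 5.5.5) than in a randomised one. There is no concurrent arm in which the same handling would apply, so the percentages of subjects with DAA-related or ribavirin-related events are read at face value.

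**Working it through.** The plan states no figure on this point, so there is nothing to reproduce. The check compares the two rules, case by case, for one subject and one preferred term.

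| Occurrences of the term | SAP 11.2.1.1 | Protocol 6.3 |
|---|---|---|
| (a) relationship missing only | unknown | associated |
| (b) missing, plus one assessed as no reasonable possibility | unknown | associated |
| (c) missing, plus one assessed as a reasonable possibility | reasonable possibility | associated |

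The documents disagree in (a) and (b) and agree in (c). Protocol 8.1.5 counts the most related occurrence and mentions no unknown category, so under the protocol (b) resolves to associated.

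**Direction.** For any row that counts subjects with related events (a preferred term, an SOC, or the overview line), let

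- R = subjects with at least one event in that row assessed as a reasonable possibility;
- U = subjects with at least one event in that row without an assessment, and none assessed as a reasonable possibility.

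The SAP count is R. The count under Protocol 6.3 is R + U. Since U ≥ 0, the SAP count is never higher, and the two are equal exactly when U = 0.

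**Size.** U cannot be computed, because neither document gives the frequency of missing causality. The SAP counts each subject once per preferred term, once per SOC and once overall. In the overview line, a subject with any other event assessed as a reasonable possibility is therefore already in R. The share of subjects with any unassessed event is only an upper bound on the change in that line.

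**Which tables.** In the maximum-relationship table, cases (a) and (b) are displayed as unknown, so a reader can add that row to the reasonable-possibility row for each term. The other related-event summaries are defined by the reasonable-possibility label alone. That unassessed events drop out of them is inferred from this definition and from SAP 6.3: "No data will be imputed for any efficacy or safety analyses except for the PRO questionnaires, for analyses of the HCV RNA endpoints", with the persistence of resistance as the one further exception. It is not stated outright. In the maximum-severity table for DAA-related events the total per term behaves as above. Individual severity rows could also shift if the unassessed occurrence is the more severe one.

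**The case against.** Four points can be made for the SAP.

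1. **Different assessors.** The SAP table reports what the investigator recorded, while the protocol sentence says what the sponsor will consider. A table with an unknown row is a faithful record of the former. This has some force. But the default exists precisely for the case where the investigator gave no assessment, and Protocol 6.3 does not confine it to serious events or to case reporting. The investigator wording is also attached only to the maximum-relationship table, so it does not explain the other summaries.

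2. **No imputation of safety data.** Protocol 8.1 and SAP 6.3 both say this, so part of the tension lies inside the protocol. That stands. Yet Protocol 6.3 is a classification rule that names its result, and applying it is not statistical imputation. SAP 11.2.1 itself uses a conservative default for another incomplete attribute: an event with a partial onset date is taken as treatment-emergent unless other evidence contradicts it.

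3. **Nothing is hidden.** This is true of the maximum-relationship table. It is not true of summaries that have no unknown row.

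4. **There may be no such events.** Protocol 10.2 has the eCRFs reviewed for completeness, and SAP 4.4 locks the data after cleaning. This stands. A reader might infer that the related-event rates will be too low, or by how much. The documents support neither: the shortfall is conditional on unassessed events surviving to lock, and any figure would rest on an assumed rate with no source in either document.

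**Conclusion.** The inconsistency is real and its direction is certain. Wherever a treatment-emergent event lacks a causality assessment at lock, the SAP's count of subjects with related events is equal to or lower than the count under Protocol 6.3. The size is unknown and may be zero. Efficacy, alpha and power are untouched.

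The conclusion rests on two readings: that the Protocol 6.3 default applies to tabulation, since the text sets no limit on it, and that summaries labelled as reasonable possibility leave out unassessed events, since nothing brings them in. It would go too far to say that the SAP expressly removes these events from every related-event table. Its rule on unknowns is written only for the maximum-relationship table, where the subjects remain visible. The point still deserves correction before lock, because two written rules for the same record conflict and the remedy is small.

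**What to change.** Replace the unknown-relationship rule in SAP 11.2.1.1 with one that applies to all relationship summaries: the overview lines, SOC and preferred-term tables, preferred-term tables, maximum severity and maximum relationship. An event whose relationship is missing or not assessable counts as a reasonable possibility for each study drug the subject actually received.

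The restriction to drugs received is needed. Genotype 1b subjects without cirrhosis take no ribavirin (Protocol Table 5, SAP Table 1). If their ribavirin field is blank, an unrestricted rule would turn their events into ribavirin-related ones.

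Footnote in each table how many subjects were assigned this way. Change the investigator-assessed label to say that unassessed events follow the Protocol 6.3 default. A cross-reference to Protocol 6.3 in the SAP's missing-data section would remove the apparent clash with the no-imputation statement.

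If the sponsor prefers to keep the unknown category, the minimum is to justify the departure and add a sensitivity count with unknowns taken as related.

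The cost is a short SAP edit, a derivation that also checks which drugs each subject received, and a footnote. The only downside is that the related-event percentages may become slightly less favourable.
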